#### **C.6 Visit Protocols and Study Measures.**

**C.6.1 Screening & consent visit:** This visit will entail informed consent and confirmation of full study eligibility in order to proceed with subsequent test visits. An interview with a trained research coordinator will determine whether any medical conditions, psychiatric disorders or medication usage may render them ineligible to continue participation. Peripheral blood glucose will be tested by glucometer to detect potential undiagnosed diabetes (random glucose  $\geq 200$  mg/dl). Those considered eligible to continue participation will be provided instructions to complete an online survey at home before their first test study visit. This will assess maternal sociodemographic factors, psychosocial states (e.g. chronic stress, anxiety, resiliency) and behaviors (e.g. usual dietary intake, sleep, exercise habits). A standardized healthy evening meal of medium GI will be delivered to participant homes prior to each test study visit to control for recent dietary influences on morning glycemia.

**C.6.2 Test visit 1:** Participants will attend the research lab facility in the morning following an overnight fast (minimum 8 hours), between 20-22 week's gestation. A research nurse will place an indwelling catheter to the antecubital vein to allow frequent blood sampling throughout the test period with minimal discomfort. After catheter placement, women will rest comfortably for 30 mins. A fasting blood and saliva sample will be collected immediately prior to consumption of the assigned standardized breakfast meal, followed by performance of either the psychosocial stress or non-stress protocol. Postprandial blood and saliva samples will be collected at +30 (pre-task), 45 (post-task), 60, 75, 90, 120 & 150 mins. A heart rate variability monitor will be worn throughout the

duration of each test study visit. Immediately pre- and post-task protocols, participants will complete questionnaires to assess momentary affective state and self-appraisal of upcoming/completed tasks.

**C.6.3 Test visit 2:** All participants will be allowed a 1-week “wash-out” period before returning to the research lab for test visit 2. Participants will undergo the same protocol as test visit 1 with the same meal assignment, except with the alternative stress/non-stress paradigm as performed on visit 1.

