Statistical Analysis Plan: Emotion-Diet Interactions in Pregnancy (PREDIP)

NCT04430439

Date of document: 4/6/2020

STATISTICAL DESIGN AND POWER ANALYSIS

Statistical Design: The statistical approach for each of the Specific Aims will be performed as follows:

Aim 1a: A cross-over study design will test the hypothesis that experimental exposure to a standardized psychosocial stress task will potentiate the postprandial metabolic response to the standardized meal. Each subject will represent her own control within the assigned meal group (low or high GI). A paired-samples t-test will be employed, using the model: $E[Y_i] = \Delta AUC_i = (AUC_i)v1 - (AUC_i)v2$

where Y_i denotes the outcome measurement (change in $AUC_{glu/ins}$ or AUC_{FFA}) on maternal i, and AUC_i denotes the AUC for either metabolic outcome at a given laboratory visit; v1 or v2. As such, a test of the hypothesis that the above equations equals 0, represents a test that the effect of acute psychosocial stress exposure does not moderate the postprandial response to a standardized meal. A sensitivity analysis to estimate the difference in response by randomization sequence will ensure that the order of protocols does not confound the results.

Aim 1b: To explore the difference in the postprandial metabolic response following acute psychosocial stress exposure across meal types (low vs high GI), an independent sample t-test will be employed to compare the mean $AUC_{glucose/insulin}$ between the high GI and low GI groups.

Aim 2: To determine whether individual variation in biological stress reactivity (i.e., $AUC_{cortisol}$ and AUC_{HRV}) moderates the effect of acute psychosocial stress on the metabolic response to the standardized meal, a general linear model accounting for within subject correlation will be employed, according to the model:

$$E[Y_{ij}] = \beta_0 + \beta_1 STRESS_{ij} + \beta_2 REACT_{ij}$$

where Y_{ij} denotes the outcome change in the AUC_i on maternal i, STRESS denotes the condition of exposure (stress vs no stress) to mother i on laboratory visit j, and REACT denotes stress reactivity, measured by $AUC_{cortisol}$ or AUC_{HRV} . A test of $H_0: \beta_1 = 0$ will test the hypothesis that mean AUC_i ($AUC_{glu/ins}$ and AUC_{FFA}) differs by stress condition after adjustment for stress reactivity. An exchangeable correlation matrix will be assumed in the model.

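### Aim 2: beta1 is adjusted for a visit-level cortisol or HRV AUC recorded largely after the task, so as written it is not the total stress effect

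*SAP*

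**What the plan says.** The SAP (Statistical Design, Aim 2) sets out to learn whether individual variation in biological stress reactivity "moderates the effect of acute psychosocial stress on the metabolic response to the standardized meal". The model is additive: E[Y_ij] = beta0 + beta1 STRESS_ij + beta2 REACT_ij, with no product term. The definitions read "STRESS denotes the condition of exposure (stress vs no stress) to mother i on laboratory visit j, and REACT denotes stress reactivity, measured by" AUC cortisol or AUC HRV. The hypothesis tested is beta1 = 0, described as testing whether mean AUC for glucose/insulin and FFA "differs by stress condition after adjustment for stress reactivity". On within-woman correlation the SAP states: "An exchangeable correlation matrix will be assumed in the model".

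Protocol C.6.2 fixes when REACT is observed. A fasting blood and saliva sample precedes the meal, and then: "Postprandial blood and saliva samples will be collected at +30 (pre-task), 45 (post-task), 60, 75, 90, 120 & 150 mins". For HRV: "A heart rate variability monitor will be worn throughout the" whole of each visit. C.6.3 repeats the protocol at visit 2 with the other task, so REACT exists at both visits. C.6.4 describes the stress task as one that induces psychosocial stress.

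Aim 1a is a separate within-woman comparison of AUC between visits, without REACT. The SAP's Power Analysis names the stress versus non-stress difference as the primary outcome and gives power for that only.

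**The concern.** Randomised task order protects the plain stress versus non-stress contrast. It does not protect a contrast made at equal values of something the task itself changes. If the task raises cortisol and cortisol raises postprandial glucose, then comparing visits at the same cortisol AUC removes that route from beta1. A null beta1 then cannot separate two opposite conclusions: stress does nothing to the metabolic response, or stress acts through the stress response the study is about.

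There is a second problem. Anything specific to a day (poor sleep, for example) that moves both REACT and the metabolic AUC biases beta1 even as a direct effect, and the documents give no basis for the direction.

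This is distinct from the missing moderation term. Adding STRESS x REACT_ij while REACT stays visit-level still leaves the STRESS coefficient conditional on a post-task variable.

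**Working it through.** **Timing.** There are eight saliva points per visit: fasting and +30 before the task; 45, 60, 75, 90, 120 and 150 min after it. That is 2 of 8 before and 6 of 8 after, with none listed during the 15-minute task. HRV covers before, during and after. The SAP gives no AUC window, so pre-task values may enter REACT. "Largely post-task" is as far as the documents go.

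**The plan's own figure.** The SAP gives about 80% power for 0.44 SD of the within-woman change with 40 women. Alpha and sidedness are not stated; 0.05 two-sided is assumed. Normal approximation: 0.44 x sqrt(40) = 2.783, and Phi(2.783 - 1.960) = 79.5%. It reproduces (noncentral t: 77.4%). It belongs to the unadjusted contrast; no power is stated for Aim 2.

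**Assumed inputs, none in the documents.** Total stress effect 0.44, in units of the SD of the within-woman difference in metabolic AUC. Share m running through REACT: 0, 0.5 or 1. Shift k in REACT caused by stress, in SDs of the within-woman difference in REACT: 0.8 or 1.5. One set of runs used a shift of 1 visit-level SD, which is k = 1/sqrt(2) = 0.71. No dropout and no period effect.

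**What beta1 estimates.** With no shared causes, beta1 = (1 - m) x 0.44:
- m = 0: 0.44
- m = 0.5: 0.22
- m = 1: 0

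**Why precision also falls.** Regressing the within-woman difference in Y on that in REACT gives SE(beta1) = s x sqrt((1 + k^2)/n), where s^2 = 1 - (m x 0.44/k)^2. The factor sqrt(1 + k^2) is the collinearity cost. Example with k = 0.8, m = 0.5, n = 40: s = 0.961, SE = 0.961 x sqrt(1.64/40) = 0.195, 0.22/0.195 = 1.13, power about 20%. With an effect of 0.22 and no collinearity, power would be Phi(0.22 x sqrt(40) - 1.960) = 28%. The exchangeable model in the SAP also uses some between-woman information, so its simulated rates differ somewhat from this formula.

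**Simulated rejection rates, exchangeable correlation** (2,000 runs per setting for k = 0.8 and 1.5; 600 for k = 0.71):

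| Share mediated | Mean beta1 | Adjusted, n = 40 | Adjusted, n = 80 | Unadjusted, n = 40 / n = 80 |
|---|---|---|---|---|
| None | 0.44-0.45 | 47-69% | 77-94% | 78-79% / 97-99% |
| Half | 0.21-0.22 | 16-27% | 26-43% | 76-79% / 97-98% |
| All | about 0 | 4-6% | 5-6% | 78-79% / 97-98% |

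The first row shows that collinearity alone costs power, so the drop in the second row is not all mediation.

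**Shared same-day causes.** In the within-woman regression, a residual correlation r between REACT and Y shifts beta1 by about -r x k. With k = 0.71 and r = +0.25 the shift is -0.18; with r = -0.25 it is +0.18. Simulation agrees. At r = +0.25 with no direct effect, beta1 averaged -0.18 in the within-woman regression and -0.11 to -0.12 in the exchangeable model. At r = -0.25 it rose to 0.62 with nothing mediated (truth 0.44) and 0.17 with everything mediated (truth 0).

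**If REACT is one value per woman.** In the additive model, STRESS is then orthogonal to REACT within each woman and beta1 keeps the total effect. Simulated at n = 40 with full mediation: 0.43, detected in 75%, the same as unadjusted.

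**The case against.** The strongest reply is that the total stress effect is already tested elsewhere. Aim 1a does not use REACT, and the stated primary outcome and power refer to the stress contrast. A reader might infer that the trial gives up its randomised stress comparison. The documents do not support that: the harm stays inside Aim 2. One reservation is that Aim 1a is written as visit 1 minus visit 2 while task order is randomised, so it does this job only if computed as stress minus non-stress.

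Second, the point leans on one subscript in loose notation. The aim speaks of individual variation, which suggests a woman-level trait, and Y_ij is called a change although it carries a visit index. This stands as a real ambiguity. But no woman-level score is defined anywhere, so the SAP needs a change on either reading.

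Third, the SAP sentence carries its qualifier about adjustment and nowhere calls beta1 confirmatory. A reader might infer that a null beta1 is bound to be reported as no stress effect; that is a prediction, not something the plan says. What remains is that the plan neither calls beta1 a direct effect nor states the assumption a direct effect needs.

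Fourth, a reader might take the figures as showing that beta1 will be null or have the wrong sign. They do not. The mediated share, the shift in REACT and the residual correlation are all assumed, and reversing the sign of that correlation reverses the bias.

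**Conclusion.** The point holds for Aim 2 as written. With REACT indexed by visit, beta1 is not the total effect of stress and cannot by itself tell no stress effect from an effect carried by cortisol or HRV. How far it departs depends on the mediated share, which is unknown. Under the assumptions above, a total effect of 0.44 SD becomes about 0.22 at half mediation and about 0 at full mediation. Bias from shared causes may add or subtract.

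The conclusion rests on REACT varying by visit and on its AUC including post-task values. It does not reach Aim 1a or the primary outcome. Nor does beta1, under either definition of REACT, answer the moderation question that Aim 2 asks.

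**What to change.** 1. Define REACT first: its AUC window, and one value per woman (for example, her stress minus non-stress difference in AUC).
2. Make the STRESS x REACT interaction the Aim 2 test. Centre REACT at its mean. With the uncentred difference score, the STRESS coefficient would be the effect at zero reactivity, which in the within-woman regression is the same adjusted coefficient again. Report the interaction as an association, since shared same-day causes can affect it too.
3. State that beta1 from a model containing visit-level REACT does not test whether mean AUC differs by stress condition. Take stress-effect claims only from the stress minus non-stress contrast without post-task variables.
4. If the visit-level adjusted beta1 is kept, label it an exploratory direct effect, state the assumption of no shared causes of REACT and the metabolic AUC, and print it beside the unadjusted coefficient.

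The cost is SAP wording and one extra model fit per outcome, with no new data. A difference score does need both visits from each woman. What is given up is reading the adjusted beta1 as the stress effect.

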**C.6.4 Experimental stress/non-stress paradigm:** The TSST is a standardized, validated experimental procedure to effectively induce psychosocial stress among healthy adults, including pregnant women. The TSST takes 15 mins to complete and involves a 5 min speech preparation, 5 min speech performance under stern observation of an evaluative committee while being video-taped, and 5min complex verbal arithmetic task. For the control non-stress condition, women will have a relaxed 15 min conversation with a familiar researcher.

**C.6.5 Test meal composition:** Test meals will be prepared by research staff under direction of the study PI, a registered dietitian. Both types of test meals will have comparable caloric content but will vary in fiber, carbohydrate and fat content to alter the GI value (*Table 1*). The pre-visit standard evening meals will have a medium GI value. All participants will be asked about food allergies or intolerances and the meals will be adapted as appropriate, while maintaining an equivalent energy content and macronutrient distribution.

**Table 1:** approximate nutritional composition of standard evening and test visit meals

	Standard pre-visit evening meal	Low GI test meal	High GI test meal
Energy, kcal	600	300	300
% carbohydrate	55	47	76
% protein	15	19	13
% fat	30	33	12
Fiber, g	15	4.5	0.7

**C.6.6 Bio-sample processing and analysis:** Fasting and postprandial blood samples will be centrifuged at 1500rpm for 15min and the separated plasma aliquoted to microtubes. All plasma and saliva will be stored at -80°C until analysis. Plasma will be assayed for glucose and insulin and saliva for cortisol by ELISA. Plasma FFA will be measured by LC-MS/MS. HOMA-IR will be computed from fasting glucose and insulin values and Adipo-IR from fasting insulin and FFA values. The AUCglu/ins and AUCFFA will be determined for each visit.

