**C.6.7 Randomization procedures:** A biostatistician will generate the randomization sequence for a 1:1 assignment to the meal group arms (*i.e.* high GI or low GI), and for the sequence of stress or non-stress protocols at the test study visits (*i.e.* stress at v1 and non-stress at v2, or non-stress at v1 and stress at v2) within each arm. Randomization sequences will be contained in sealed, opaque envelopes labeled by sequential study IDs and only revealed by research coordinators after completion of a screening visit for a fully eligible participant.

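### The Aim 2 model has no meal or visit term, so its tested stress coefficient can be biased if the meal itself shifts cortisol or HRV as well as the metabolic AUC

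*SAP*

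**What the plan says.** For Aim 2 the SAP (Statistical Design, Aim 2) states that "a general linear model accounting for within subject correlation will be employed, according to the model" E[Y] = beta0 + beta1 STRESS + beta2 REACT, indexed by woman i and visit j. It then says "An exchangeable correlation matrix will be assumed in the model". The stated test is of beta1 = 0, described as whether the mean AUC "differs by stress condition after adjustment for stress reactivity". REACT is the AUC of cortisol or of HRV and carries the visit subscript.

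MEAL, visit and sequence do not appear in the equation. Aim 1a, by contrast, is framed within the assigned meal group, and its sensitivity analysis by sequence is stated only there.

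In the protocol, C.2 randomises 80 women between meals, 40 per arm. C.6.7 randomises the meal arm "and for the sequence of stress or non-stress protocols at the test study visits" within each arm. C.6.5 says that the meals "will vary in fiber, carbohydrate and fat content to alter the GI value"; Table 1 gives 76% against 47% carbohydrate. On timing, C.6.2 says "Postprandial blood and saliva samples will be collected at +30 (pre-task), 45 (post-task), 60, 75, 90, 120 & 150 mins", with one fasting sample before the meal and the HRV monitor worn throughout.

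**The concern.** A between-woman factor can usually be left out of a cross-over analysis, because each woman is her own control and the factor cancels from the stress contrast. That argument holds when STRESS is the only regressor. Here beta1 is tested after adjustment for REACT, a covariate measured largely after the meal. Part of beta2 is estimated from differences between women, and the meal is a difference between women. If high-GI women have both a different metabolic AUC and a different cortisol or HRV AUC, beta2 picks up an association that belongs to the meal. Because stress is meant to change REACT, the error in beta2 then passes to beta1.

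At stake are the size, power and error rate of the one coefficient that Aim 2 tests, and any reading of beta2 as a reactivity association. Visit effects can act by the same route.

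**Working it through.** **The plan's own figure.** The only power statement is for the paired comparison: 40 women per meal group, 0.44 SD, about 80%. With two-sided alpha 0.05 (assumed; not stated), 0.44 × √40 − 1.960 = 0.823, and Φ(0.823) = 79.5%; the exact paired t gives 77.5%. The figure is reproduced. It does not cover Aim 2, for which no power is given.

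**Step 1: how beta2 reaches beta1.** Take Y as the AUC at each visit. For each woman form the mean over her two visits and the stress-minus-control difference. Then

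estimated beta1 = mean difference in Y − beta2 × mean difference in REACT.

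**Step 2: what beta2 estimates.** With exchangeable correlation ρ, the woman means have weight Wb = 2/(1+ρ) and the differences Ww = 1/[2(1−ρ)]. Let the meal shift Y by g and REACT by m (SD units), with half the women on each meal, true beta2 = 0, and within-woman correlation r of REACT. Without MEAL in the model, beta2 tends to

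Wb·(g·m/4) / {Wb·[(1+r)/2 + m²/4] + Ww·2(1−r)}.

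This is zero if g = 0 or m = 0. The omitted meal variance also raises the working correlation, from ρ0 to (ρ0 + g²/4)/(1 + g²/4).

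**Step 3: numbers.** All effects are assumed: ρ0 = 0.5, r = 0.5, stress shifts REACT by 1 SD, true beta1 = 0.30. For g = 1, m = 0.5:
- ρ = 0.75/1.25 = 0.60, so Wb = 2/1.6 = 1.25 and Ww = 1/0.8 = 1.25.
- beta2 = 1.25 × 0.125 / [1.25 × 0.8125 + 1.25 × 1] = 0.156/2.266 = 0.069.
- beta1 = 0.30 − 1 × 0.069 = 0.231, which is 23% too small.

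The table sets the formula beside simulations of 80 women with an exchangeable GEE and sandwich SEs (repeated runs of 1,500 to 4,000 trials).

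| g (meal on AUC) | m (meal on REACT) | ρ0 | beta1, formula | beta1, simulated |
|---|---|---|---|---|
| 0.5 | 0.3 | 0.5 | 0.276 (8% low) | 0.275–0.278 |
| 1 | 0.3 | 0.5 | 0.258 (14% low) | 0.256–0.264 |
| 1 | 0.5 | 0.5 | 0.231 (23% low) | 0.226–0.231 |
| 1 | −0.5 | 0.5 | 0.369 (23% high) | 0.368–0.373 |
| 1 | 0.5 | 0.8 | 0.266 (11% low) | 0.263–0.265 |
| 1 | 0.5 | 0.2 | 0.207 (31% low) | not run at 1 SD |
| 1 | 0 | 0.5 | 0.300 (none) | 0.30 |

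With MEAL in the model, simulated beta1 is 0.298 to 0.305 for the positive shifts at ρ0 = 0.5.

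**Step 4: power and error rates.** At g = 1, m = 0.5, power for beta1 = 0.30 is about 38%, against about 61% with MEAL. With true beta1 = 0, the false-positive rate for beta1 is about 9%, against about 6% with MEAL. At g = 1, m = 0, the SE of beta2 is 0.083 without MEAL and 0.077 with it: 0.083/0.077 = 1.08.

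**Step 5: visit.** A visit effect on Y alone causes no bias. Opposite visit effects of 0.3 to 0.5 SD on Y and REACT (stress effect on REACT 0.8 SD) bias beta1 by +0.03 to +0.08, with 5.9% to 7.5% false positives. Adding visit removes the bias.

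**The case against.** The strongest reply is that a reader might infer that the meal difference does leak into the stress coefficient, and the documents do not show this. Meal is randomised and task order is randomised within arm, so STRESS is balanced over meal. Bias in beta1 needs three things together: the meal shifts the metabolic AUC, the meal shifts the cortisol or HRV AUC, and REACT varies by visit and responds to stress. The meal design makes the first plausible, and the purpose of the stress task supports the third. The second is possible because REACT is measured mostly after the meal, but no figure in either document supports it. This objection stands, and it makes the point conditional.

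Two readings of the SAP also matter. Pooling is inferred from the absence of an arm restriction; if Aim 2 is fitted within each arm, the meal route disappears. If REACT is one value per woman, as the phrase about individual variation might suggest, beta2 can still be biased but beta1 is not. The visit subscript favours the per-visit reading.

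A reader might also infer that Aim 2 ignores both randomised factors. That goes too far: STRESS is itself the randomised task at each visit, so it carries the order allocation. What is missing is the visit effect.

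Finally, a STRESS x MEAL term is not needed to remove the bias, and it can do harm. With 0/1 coding, beta1 becomes the stress effect in one meal arm, and in the g = 1 scenario its power falls from 61% to about 42%; centred coding keeps about 62%. This stands and shapes the fix.

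**Conclusion.** The omission is real, and its consequence is conditional. As written, and read as pooled with per-visit REACT, the Aim 2 model leaves beta1 open to bias if the meal affects REACT. Under the assumed effects at correlation 0.5, a true 0.30 is understated by about 8% to 23%, with about 9% false positives against 6% in the worst of these cases. The size falls at higher within-woman correlation and rises at lower. The error need not be conservative: if the meal shifts REACT and AUC in opposite directions, beta1 is inflated. With no meal effect on REACT there is no bias, and the loss is an SE of beta2 about 8% larger. The documents do not support a claim that the Aim 2 result will be biased, or by how much.

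The change should be made because it removes the exposure at almost no cost. Confidence is medium, since the effect sizes are assumptions.

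**What to change.** State in the SAP whether Aim 2 pools the meal arms and whether REACT is per visit. If pooled, add MEAL and visit (period) as main effects to the Aim 2 model for every outcome, keeping the exchangeable correlation. If it is fitted within arm, say so and add visit.

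If STRESS x MEAL is also wanted, code MEAL as −0.5/+0.5, so that the test of beta1 = 0 still concerns the stress effect averaged over arms.

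The cost is SAP wording and two degrees of freedom, or three with the interaction, out of 80 × 2 = 160 woman-visits. No extra data are needed, because meal and visit are known from the design.

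This does not repair a separate gap: Aim 2 asks about moderation, but the equation has no STRESS x REACT term.

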**Study Protocol: Emotion-Diet Interactions in Pregnancy**

**NCT04430439**

**Date of Document: 10/20/2022**

**C.1 Overview.** This research will represent the first investigation of objectively measured diet-stress interactions in human pregnancy, thus providing critical insight to the contribution of psychosocial stress in influencing important gestational metabolic pathways that have implications for maternal and child health and disease risk. The working hypothesis is that acute psychosocial stress will exacerbate the postprandial plasma glucose/insulin and free fatty acid (FFA) response to a standardized meal, and that this response will be exaggerated after consumption of a high GI versus a low GI meal. The overall strategy is to enroll a cohort of non-diabetic pregnant women with overweight and obesity to test the postprandial metabolic response to a standardized meal of varying GI, with and without psychosocial stress exposure.

**C.2 Study Design.** This is a two-armed, randomized, cross-over study in which N=80 women will be randomly assigned in a parallel design to either a low or high GI standardized breakfast. Within each arm, N=40 women will attend two test study visits in a randomized, cross-over design, to undergo either the TSST challenge task or a control non-stress task immediately following consumption of their assigned meal type.

**C.3 Clinical Research Setting.** The study will be performed at the PI's research facility on the UCI campus in Irvine and will utilize additional clinical facilities of the UCI Institute of Clinical and Translational Science (ICTS).

**C.4 Study Site and Population.** Subjects will be primarily recruited from UCI-affiliated clinics; the UCI Medical Center faculty private practice, and UCI-affiliated family health clinics in surrounding districts within Orange County, CA, which serve women from an urban metropolitan area encompassing a population base of over 2.75 million residents. Recent demographic profiles of this population indicate that 68% of the patients are multiparous; 65% are married, and 58% belong to ethnic minority groups (predominantly Hispanic). Over the past year, the PI has independently enrolled N=33 Hispanic women from this prenatal population.

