Power Analysis: The primary outcome of the proposed research is the difference in the postprandial glucose/insulin response to a standardized meal (of either low or high GI) between the stress and non-stress conditions. Utilizing a cohort of 40 women in each meal group, it is estimated that the proposed study will have approximately 80% power to detect a 0.44 standard deviation difference in the mean within subject change in postprandial metabolic response ($AUC_{glu/ins}$ and AUC_{FFA}), associated with the introduction of the stress paradigm.

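### The SAP does not say whether Aim 1a is one paired test in 80 women or two in 40; its power figure fits only 40 pairs, and one meal-stratified test would detect about 0.32 SD

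*SAP*

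**What the plan says.** Protocol C.2 sets out the design: "N=80 women will be randomly assigned in a parallel design to either a low or high GI standardized breakfast", and then "Within each arm, N=40 women will attend two test study visits in a randomized, cross-over design". C.6.7 randomizes both the meal arm (1:1) and the order of the stress and control visits. Under C.6.3 each woman has the same meal assignment at both visits.

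The hypothesis about stress is stated in general terms in C.1: "acute psychosocial stress will exacerbate the postprandial plasma glucose/insulin and free fatty acid (FFA) response to a standardized meal". C.1 adds a second expectation, that the response will be larger after the high-GI meal.

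SAP Aim 1a names a paired t-test and says "Each subject will represent her own control within the assigned meal group (low or high GI". It writes the difference as the AUC at visit 1 minus the AUC at visit 2. The Power Analysis reads "Utilizing a cohort of 40 women in each meal group, it is estimated that the proposed study will have approximately 80% power"; the effect size attached to this claim is 0.44 SD. It describes the primary outcome as the stress versus non-stress difference after a meal of one GI type or the other.

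Neither document says whether the two meal arms are tested separately or together. No alpha, sidedness or dropout rate is given, and there is no rule for the case where the arms give different answers.

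**The concern.** The primary analysis is not fixed, and each way of reading it leaves a gap.

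- **One test in 80 women.** The power paragraph then describes a different analysis, and understates what the trial can detect.
- **One test per arm.** Each test then uses half the women, although the question is a single one. A woman's meal is the same at both visits, so it cannot confound her own stress-versus-control difference, and nothing in the design prevents a combined test. The SAP also does not say what counts as success: either arm, both arms, or some combination.

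With two separate tests, one arm may well reach p<0.05 and the other not. Because C.1 predicts a larger response after the high-GI meal, a split in that direction could be taken as confirmation. It can arise by chance when the stress effect is the same in both arms. Aim 1b does not settle this, because it is described as comparing mean AUC between meal groups after stress, not the stress-minus-control differences.

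**Working it through.** **Inputs.** From the documents: 40 women per meal arm and 80 in total (C.2; SAP Power Analysis), a paired t-test (Aim 1a), an effect of 0.44 SD of the within-woman change, and power of about 80%. Assumed: two-sided 5%, no dropout unless stated, and the same SD of the difference in both arms.

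**1. Reproduce the stated figure.** The detectable effect is d = (z₀.₉₇₅ + z₀.₈₀)/√n.
- n = 40: (1.960 + 0.842)/√40 = 0.443 SD. This is the SAP's 0.44.
- Power at 0.44 SD with n = 40: 79.5% (normal) or 77.4% (exact noncentral t, 39 df). The exact 80% point is 0.454 SD.
- Alternatives do not fit. One-sided 5% with n = 40 gives 0.393 SD. A two-sample test of 40 v 40 has 50% power at 0.44 SD. A paired test with n = 80 has 97.3%.

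So the stated power belongs to one arm of 40.

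**2. One test in all 80 women, stratified by meal.** Give each arm mean a weight of one half. The noncentrality is √80 × (average effect), with 78 df.
- 80% power at 0.317 SD (normal approximation 2.802/√80 = 0.313). Also splitting by visit order gives four cells and 80 − 4 = 76 df, and the answer is still 0.317.
- Power at 0.44 SD in both arms: 97.3%.
- With 10% loss (72 women): 0.335 SD. With 20% loss (64 women): 0.356 SD.
- At a true 0.32 SD in both arms: 51% power in each arm's test, 81% in the combined test.

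**3. Unequal effects.** Hold the high-GI effect at 0.44 SD, where that arm's own test has 77% power.

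| Low-GI effect (SD) | Average (SD) | Combined power |
|---|---|---|
| 0.44 | 0.44 | 97% |
| 0.30 | 0.37 | 90% |
| 0.20 | 0.32 | 81% |
| 0.10 | 0.27 | 66% |
| 0 | 0.22 | 49% |

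Let r be the low-GI effect divided by the high-GI effect. The combined test matches the high-GI arm's test when √80 × (1 + r)/2 = √40, so r = √2 − 1 = 0.414.

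**4. Split results under an identical effect.** With power p in each arm, exactly one arm is significant with probability 2p(1 − p).
- 0.44 SD: 2 × 0.774 × 0.226 = 35%. Both arms are significant in 60% of trials and neither in 5%.
- 0.32 SD: 50%. 0.40 SD: 42%. 0.50 SD: 23%. 0.60 SD: 8%.

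**5. Direct stress-by-meal comparison.** Comparing the differences between 40 and 40 women, 80% power needs 0.63 SD (exact t; normal approximation 2.802 × √(2/40) = 0.626).

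**6. The difference as written.** If half the women have stress first, visit 1 minus visit 2 has mean ½(+δ) + ½(−δ) = 0 whatever the stress effect δ. In simulation at 0.44 SD it rejects in about 3% of trials, with 40 or with 80 women. Steps 1 to 5 therefore hold only for a difference defined as stress minus control.

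**The case against.** A reader might infer that the SAP prescribes two separate tests. The documents do not say so. Aim 1a names a single paired t-test, the phrase about the assigned meal group may mean only that each woman has the same meal twice, and the primary outcome sentence can be read as covering both meals together. The 40-woman power figure favors separate tests, but only by implication. This objection stands, so the point is the ambiguity and its mismatch with the stated power.

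If separate tests are intended, they can be defended. C.1 expects different effects by meal, and an equal-weight average over two test meals is a different target from either meal's own effect. Nor is half the data discarded, since both arms are analyzed. With each arm tested at 2.5%, at least one is significant in 89% of trials at 0.44 SD in both arms, against 97% combined. At 0.32 SD the figures are 63% and 81%. The order reverses if the low-GI effect is 0 (68% v 49%) or 0.10 SD (69% v 66%). This also stands, as the price of the fix. But a larger response after high GI does not mean no response after low GI, and a plan for two tests would still need a decision rule, which the SAP lacks.

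A reader might also infer that the arms would contradict each other in a third of trials. That figure holds only near 0.44 SD, and it means that one arm is significant and the other is not, not that the effects point in opposite directions.

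**Conclusion.** The concern holds as a missing specification with a measurable cost. The SAP leaves open whether its primary stress test uses 80 women once or 40 women twice, and its power statement matches only the latter. For the general stress hypothesis, one meal-stratified test lowers the detectable effect from 0.454 to 0.317 SD, and it is the stronger choice unless the low-GI effect is below about 41% of the high-GI effect.

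The 0.44 in the SAP is not itself an error; it is the normal-approximation counterpart of 0.454. All figures rest on two-sided 5%, an equal SD of the difference in both arms, and a difference taken as stress minus control. They apply to one outcome at a time; the SAP lists glucose/insulin and FFA AUCs without naming a single primary measure. The documents do not support a claim that two tests are definitely planned, or that a split result will be misread. They show only that nothing in the plan guards against it.

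**What to change.** In SAP Aim 1a:

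1. Define each woman's difference as AUC under stress minus AUC under control, replacing visit 1 minus visit 2. The power below depends on this.
2. Make the primary analysis one two-sided 5% test of the mean difference over all 80 women, stratified by meal arm (arm means weighted one half each) and adjusted for sequence/period. Name the outcome to which it applies.
3. As a secondary analysis, compare the stress-minus-control differences between the meal arms. State that about 0.63 SD is detectable with 40 v 40, so a non-significant result does not show equal effects.
4. Report both arm-specific estimates with confidence intervals, and say that significance in one arm only is not evidence of an interaction.

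In the Power Analysis, state alpha, sidedness and the assumed loss. Then give 80% power for an average stress effect of about 0.32 SD with 80 women (about 0.335 SD with 10% loss), and about 97% power at 0.44 SD.

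The change needs no new participants or data. Its cost is lower power if stress acts only after the high-GI meal: about 49% at 0.44 SD v 0, against 77% for that arm's own test. If the sponsor prefers meal-specific primary tests for that reason, the SAP should say so, keep the 40-woman power figure, and state how the two results are combined and how error is controlled.
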